14 FINANCIAL DISCLOSURE AND CONFLICT OF INTEREST POLICY

A separate financial disclosure agreement will be made between each principal investigator and Alkahest, Inc. or its authorized representative before the study agent is shipped. Each investigator will notify Alkahest, Inc. or its authorized representative of any relevant changes during the conduct of the study and for 1 year after the study has been completed. Alkahest and the study CRO will evaluate any disclosed conflicts of interest and will establish a mechanism for their management.

15 SCHEDULE OF EVENTS

	Screening/ Baseline		Treatment			EOT	Safety Follow-up ⁶
Visit Number/Name	1	2	3 ¹	4 ²	Unsched. Visit ⁴	5 ³ / EOT ⁵ 21 or Dis. Control ±2 ³ Up to 3	Follow-up EOT + 14 ±3 Up to 5
Day	-3 to 0	1	7	14			
Window (days)			±2	±2			
Week			1	2			
Informed consent ⁷	X						
Demographics	X						
Medical history	X						
Inclusion/exclusion criteria	X	X ⁸					
Physical examination	X					X	
Targeted physical examination		X	X	X			
Vital signs	X	X	X	X		X	
12-lead ECG	X						X
BPDAI	X	X	X	X			X
BPDAI-VAS	X	X	X	X			X
Skin biopsy ⁹	X						X
Blister fluid collection		X	X				
Randomization		X					
Topical steroid assessment ¹⁰		X			X		
Administration of study agent		↔					
Administration of topical steroid therapy		↔					
Assessment of disease control ¹¹			X	X	X	X	
Rescue therapy assessment ¹²			X	X	X		
MoCA		X					X
DLQI		X					X
Laboratory tests ¹³	X	X	X	X			X
Serum protein sample collection	X	X	X	X			X
Anti-BP180 antibodies sample collection	X	X	X	X			X
Pregnancy test (in WOCBP only) ¹⁴	X						X
PK blood sample ¹⁵		X	X	X			X
Biomarker plasma aliquots ¹⁶		X					X
Study agent accountability ¹⁷		X	X	X	X		X
Adverse events	X	X	X	X	X	X	X
Concomitant medications ¹⁸	X	X	X	X	X	X	X
Documentation of confirmation of histological BP diagnosis						X	
Trial completion							X

Notes:

1. At Visit 3/Week 1, all subjects that have not achieved disease control will be assessed for rescue therapy. Rescue therapy is indicated if the subject worsens at any time during the study or fails to improve by the end of Week 1, as assessed by the investigator.
2. After Visit 3/Week 1, subjects will continue to be assessed weekly until disease control/EOT visit.
3. Subjects that do not reach disease control by the end of Week 3/Visit 5 will be discontinued and required to perform all EOT visit procedures. Visit 5 will be the EOT visit for subjects that reach Week 3, and all EOT procedures will be performed. The visit window of \pm 2 days is applicable only for subjects that did not yet reach disease control and are being discontinued. Subjects that reach disease control should complete EOT on the same day in which disease control is confirmed.
4. Unscheduled visits can be performed during the study for assessment of AEs, concomitant medications, or disease control, but are not to be conducted in place of a scheduled weekly visit.
5. All EOT visit procedures will be conducted at any point in the study once the subject has achieved disease control. This may be performed outside of the scheduled weekly visits and in place of the next scheduled visit.
6. Trial completion will occur after the completion of the Safety Follow-up call. The Safety Follow-up call should occur 14 days \pm 3 days following the EOT visit, independent of the actual study day number.
7. All subjects must sign an informed consent consistent with ICH GCP guidelines prior to any trial related procedures, which includes medication washouts and restrictions.
8. At Visit 2/baseline, confirmation of all inclusion and exclusion will be required prior to enrollment in the study.
9. Skin biopsy at screening is required for subsequent confirmation of diagnosis. Skin biopsies at disease control will be performed only if blisters are present and are optional.
10. At baseline, subjects will be assessed by the investigator to assign the initial dose of topical MFC. The dose selected at baseline will be the same dose used throughout the study, unless the subject requires rescue therapy.
11. Disease control is defined as: \leq 3 new blisters/day and healing of existing blisters. Assessment of disease control will be performed during scheduled weekly visits by the investigator, as per protocol. Additional assessments performed daily as part of SOC will be reviewed by the site staff at each study visit to monitor disease progression between visits. SOC assessments of disease control will be collected and recorded, as available.
12. Rescue therapy can be provided at any time after enrollment if the subject's clinical condition worsens OR fails to improve after completing 1 week of treatment, as determined by the investigator.
13. Laboratory tests include: hematology; chemistry; serology (HBV, HCV, HIV, and TB); coagulation; urinalysis. Note: serology will only be conducted at screening. See [Section 7.1.1.2.6](#) for more details.
14. Serum pregnancy test will be collected at screening and end of treatment in WOCBP.
15. At Baseline (Visit 2) PK samples will be required to be collected pre-dose and 1 hour (\pm 15 minutes) after administration of the first dose. Additionally, optional PK samples may be collected at 2 hours (\pm 30 minutes) after administration of the first dose and 4 hours (\pm 30 minutes) after administration of the first dose. All PK samples collected during the scheduled weekly visits will be drawn within 1 hour prior to the morning (am) dose. At the EOT visit, the sample will be collected at any time during the visit, and the time of the subject's last dose and the time of the PK sample collection will be recorded.
16. Biomarker aliquots will be taken from the PK samples, as described in the Laboratory Manual.
17. Includes all study agents (AKST4290, MFC, and CPC and /or oral prednisone).
18. [REDACTED]

17 APPENDICES

The BP assessments, cognitive assessment and quality of life assessment tools provided in this section and associated information are provided as EXAMPLES ONLY. The actual assessments, related source documents, and instructions for administration and scoring are included in a rater reference manual or equivalent.

17.1 BULLOUS PEMPHIGOID DISEASE AREA INDEX TOOL

BPDAI					
SKIN	ACTIVITY		ACTIVITY		DAMAGE
Anatomical location	Erosions/Blisters	Number of Lesions if <3	Urticaria/ Erythema / Other	Number of Lesions if <3	Pigmentation / Other
	0 absent		0 absent		Absent 0, present 1
	1 1-3 lesions, none > 1 cm diameter		1 1-3 lesions, none >6 cm diameter		
	2 1-3 lesions, at least one > 1 cm diameter		2 1-3 lesions, at least one lesion > 6 cm diameter		
	3 >3 lesions, none > 2 cm diameter		3 >3 lesions, or at least one lesion > 10 cm		
	5 >3 lesions, and at least one >2 cm		5 >3 lesions and at least one lesion > 25 cm		
	10 >3 lesions, and at least one lesion >5 cm diameter or entire area		10 >3 lesions and at least one lesion > 50 cm diameter or entire area		
Head					
Neck					
Chest					
Left arm					
Right arm					
Hands					
Abdomen					
Genitals					
Back/Buttocks					
Left leg					
Right leg					
Feet					
Total skin	/120		/120		
MUCOSA	Erosions/Blisters				
	1 1 lesion				
	2 2-3 lesions				
	5 >3 lesions, or 2 lesions >2cm				
	10 entire area				
Eyes					
Nose					
Buccal mucosa					
Hard palate					
Soft palate					
Upper gingiva					
Lower gingiva					
Tongue					
Floor of Mouth					
Labial Mucosa					
Posterior Pharynx					
Anogenital					
Total Mucosa	/120				

[figure not shown]
17.2 BULLOUS PEMPHIGOID DISEASE AREA INDEX TOOL - VISUAL ANALOG SCALE

BPDAI PRURITUS COMPONENT - VAS

DATE:

[figure not shown]
 Baseline	 Beginning Consolidation
 Consolidation phase	 End of Consolidation
 Tapering phase	 Partial remission on minimal therapy
 Complete remission on minimal therapy	 Partial remission off therapy
 Complete remission off therapy	 Flare

A. How severe has your itching been over the last 24 hours?

[figure not shown]
Score out of 10 =

B. How severe has your itching been the past week?

Score out of 10 =

C. How severe has your itching been in the past month?

Score out of 10 =

Average INTENSITY SCORE FOR PAST MONTH = (A+B+C) = /30

**PRURITIS ASSESSMENT FOR BP PATIENTS
WITH IMPAIRED MENTAL FUNCTIONING:**

No evidence of itch (no excoriations)	0
Mild itch (isolated excoriations up to two body sites)	10
Moderate itch (excoriations on \geq 3 body sites, impairment of daily activity)	20
Severe itch (generalized excoriation, sleep impairment)	30
TOTAL SCORE	/30

17.3 DERMATOLOGY LIFE QUALITY INDEX

DERMATOLOGY LIFE QUALITY INDEX (DLQI)

Hospital No:

Date:

Name:

Score:

Address:

Diagnosis:

The aim of this questionnaire is to measure how much your skin problem has affected your life
OVER THE LAST WEEK. Please tick (✓) one box for each question.

1. Over the last week, how itchy, sore, painful or stinging has your skin been?	Very much 	A lot 	A little 	Not at all 	
2. Over the last week, how embarrassed or self conscious have you been because of your skin?	Very much 	A lot 	A little 	Not at all 	
3. Over the last week, how much has your skin interfered with you going shopping or looking after your home or garden ?	Very much 	A lot 	A little 	Not at all 	Not relevant 
4. Over the last week, how much has your skin influenced the clothes you wear?	Very much 	A lot 	A little 	Not at all 	Not relevant 
5. Over the last week, how much has your skin affected any social or leisure activities?	Very much 	A lot 	A little 	Not at all 	Not relevant 
6. Over the last week, how much has your skin made it difficult for you to do any sport ?	Very much 	A lot 	A little 	Not at all 	Not relevant 
7. Over the last week, has your skin prevented you from working or studying ?	Yes 	No 		Not relevant 	
If "No", over the last week how much has your skin been a problem at work or studying ?	A lot 	A little 	Not at all 		
8. Over the last week, how much has your skin created problems with your partner or any of your close friends or relatives ?	Very much 	A lot 	A little 	Not at all 	Not relevant 
9. Over the last week, how much has your skin caused any sexual difficulties ?	Very much 	A lot 	A little 	Not at all 	Not relevant 
10. Over the last week, how much of a problem has the treatment for your skin been, for example by making your home messy, or by taking up time?	Very much 	A lot 	A little 	Not at all 	Not relevant 

17.4 MONTREAL COGNITIVE ASSESSMENT

The MoCA ([Nasreddine 2005](#)) is a commonly used screening test easily administered by nonspecialist staff. It assesses the domains of attention and concentration, executive functions, memory, language, visuoconstructional skills, conceptual thinking, calculations, and orientation. The total possible score is 30 points with a score of 26 or more considered normal. Time to administer the MoCA is approximately 15 minutes. The total possible score is 30 points.

[figure not shown]
17.5 MODIFICATION OF DIET IN RENAL DISEASE FORMULA

The GFR may be estimated based on the MDRD formula:

$$\text{GFR (ml/min/1.73 m}^2\text{)} = 186 \times [(\text{P}_{\text{cr}})/88.4]^{-1.154} \times (\text{age})^{-0.203} \times (0.742 \text{ if female}) \times (1.210 \text{ if African American})$$

Units: GFR [ml/min], age [years]

A 2D binary image (black and white) showing a sparse pattern of black pixels on a white background. The pattern is composed of several vertical columns of black pixels, with some columns being taller than others. The background is white with a fine grid of black lines, creating a pixelated or grid-based appearance. The pattern is centered and roughly rectangular in shape, with a dense cluster of black pixels on the left side and more scattered black pixels on the right side.

17.7 CLINICAL EVALUATION OF LIVER INJURY

17.7.1 INTRODUCTION

Alterations of liver laboratory parameters [REDACTED] are to be further evaluated using the procedures described below.

17.7.2 PROCEDURES

Repeat the following laboratory tests: ALT, AST, and bilirubin (total and direct) - within 48 to 72 hours and provide additional blood sample to the central laboratory for automatic reflex testing of the below listed laboratory parameters. Only in cases in which the central laboratory is not immediately available (e.g. if the logistics are such that the subject's repeat specimen would not reach the central laboratory in a reasonable timeframe), ALT, AST, and bilirubin (total and direct) will be evaluated by the local laboratory and results will be made available to the investigator and to Alkahest as soon as possible. If ALT and/or AST > 3 -fold ULN combined with an elevation of total bilirubin > 2 -fold ULN are confirmed, results of the laboratory parameters described below must be made available to the investigator and to Alkahest as soon as possible.

In addition, the following should be reported in the eCRF:

- Detailed history of current symptoms and concurrent diagnoses and medical history according to the DILI Checklist provided in the ISF
- History of concomitant drug use (including non-prescription medications, herbal and dietary supplement preparations), alcohol use, recreational drug use, and special diets according to the DILI Checklist provided in the ISF
- History of exposure to environmental chemical agents (consider home and workplace exposure) according to the DILI Checklist provided in the ISF

17.10.2.1 Clinical Chemistry

- Obtain an ALP, albumin, prothrombin time or INR, creatinine kinase, creatinine kinase-muscle/brain test, ceruloplasmin, α -1 antitrypsin, transferrin amylase, lipase, glucose, cholesterol, triglycerides

17.10.2.2 Serology

- Obtain a hepatitis A (anti-immunoglobulin M [IgM], anti-IGM), hepatitis B (hepatitis B antigen, anti-HBs, DNA), hepatitis C (anti-hepatitis C virus [HCV], RNA if anti-HCV positive), hepatitis D (anti-IgM, anti-immunoglobulin G [IgG]), hepatitis E (anti-hepatitis E virus [HEV], anti-HEV IgM, RNA if anti-HEV IgM positive), anti-smooth muscle antibody (titer), anti-nuclear antibody (titer), anti-liver-kidney microsomes antibody, antimitochondrial antibody, Epstein Barr virus (vascularized composite allotransplantation [VCA] IgG, VCA IgM), cytomegalovirus (IgG, IgM), herpes simplex virus (IgG, IgM), varicella (IgG, IgM), parvovirus (IgG, IgM), toxoplasmosis (IgG, IgM).

17.10.2.3 Hormones

- Thyroid-stimulating hormone

17.10.2.4 Hematology

- Thrombocytes, [REDACTED]

17.10.2.5 Ultrasound

- Provide an abdominal ultrasound to rule out biliary tract, pancreatic, or intrahepatic pathology (e.g., bile duct stones or neoplasm)

17.10.2.6 Observation/Repeat Testing

- Initiate close observation of subjects by repeat testing of ALT, AST, and total bilirubin (with fractionation by total and direct) at least weekly until the laboratory ALT and/or AST abnormalities stabilize or return to normal, then according to the protocol. Depending on further laboratory changes, additional parameters identified e.g. by reflex testing will be followed up based on medical judgment and GCP.

17.8 PHARMACOKINETIC AND BIOMARKER SAMPLING

17.8.1 TABLE OF PHARMACOKINETIC AND BIOMARKER SAMPLING

Visit	Time Point	Time for Database Setup	PK Blood	Extra Biomarker Aliquot from PK Blood Sample
2 (Baseline)	Prior to (i.e., within 15 min before study agent administration) REQUIRED SAMPLE	-0:15 h	X	X
	0:00	0:00 h	Study agent administration	
	1:00 hour \pm 15 minutes after administration of the first dose REQUIRED SAMPLE	1:00 h	X	
	2 \pm 30 minutes after administration of the first dose OPTIONAL SAMPLE	2:00 h	X	
	4 \pm 30 minutes after administration of the first dose OPTIONAL SAMPLE	4:00 h	X	
3 – 5 (Study Week 1 and all subsequent weekly visits until EOT)	-00:15 min (i.e., within 15 min before study agent administration)		X	
EOT	Any time during visit – preferably at the end of all visit procedures		X	X

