7.2.2.1.1 Pharmacokinetic Endpoints

As far as feasible, the following PK parameter will be summarized descriptively:

- $C_{pre,ss,N}$ Pre-dose concentration of AKST4290 in plasma immediately before administration of the Nth dose

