10.3. Data transformations and derivations

Values will be presented for all scheduled study visits according to the nominal visit obtained from the eCRF. If an unscheduled visit falls in a visit window with an existing nominal visit assessment, the nominal assessment will be used in analyses. If no nominal visit assessment exists for a visit window with unscheduled visit(s), then the first unscheduled visit within the visit window will be used.

If the End of Treatment visit is performed in place of a scheduled weekly visit, the measurements of the End of Treatment visit are also used for that scheduled weekly visit. This is assumed to be the case if the End of Treatment visit falls into the protocol-specified visit window of some scheduled visit, and that particular scheduled visit is not done.

All heights will be converted to centimeters, all weights to kilograms, and all temperatures to Celsius units.

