13.12. Quality of life

The Dermatology Life Quality index score, as well as the components used to derive the score, will be presented in a listing.

14. Pharmacokinetic analyses

Only data from the AKST4290 group will be used for pharmacokinetic analyses.

Data handling methods outlined in study protocol section 17.9.4 will be followed (missing data not included, values below lower limit of quantification replaced with zero, parameter estimates and descriptive statistics only reported when at least 2/3 data are available).

AKST4290 concentration values will be reported in a figure, table and listing by analysis time point.

15. Changes to Methods Planned in the Protocol

As detailed in the protocol, the goal was to enroll a total of approximately 30 subjects with the aim of obtaining 27 evaluable subjects. Due to the treatment limitations, rarity of the disease, coronavirus disease 2019 (COVID-19) pandemic, and expiry of Investigational Medicinal Product (IMP), enrollment ended with a total 6 subjects.

Section 10.3 (Analysis Datasets) of the clinical study protocol includes a Per Protocol (PP) analysis set defined as “a subset of ITT subjects.” This analysis set will not be utilized in the statistical analysis due to the limited enrollment noted previously and the restriction to descriptive analysis of study endpoints.

Section 10.4 (Descriptions of Statistical Methods) of the clinical study protocol outlines analysis of the primary endpoint (Section 10.4.2), secondary endpoints (Section 10.4.3) and exploratory analysis (Section 10.4.6). Due to the limited enrollment in the study, the analysis defined in Section 11 (Summary of study population), Section 12 (Safety analyses), 13 (Efficacy analyses) and 14 (Pharmacokinetic analyses) of the SAP will be utilized.

16. Top-Line Data Presentation

The following assessments associated with the study endpoints, as reported by listings, tables, and figures (where applicable), will be provided as top-line results:

- Disease Control and Rescue Therapy
- BPDAI and BPDAI-VAS
- Adverse events
- Skin biopsy [REDACTED] levels
- Steroid exposure
- Blood [REDACTED] levels

17. References

[REDACTED]	[REDACTED]	[REDACTED]	[REDACTED]	[REDACTED]	[REDACTED]
	[REDACTED]				

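### End-of-treatment PK samples, which need not be pre-dose, can enter the weekly pre-dose concentration summaries under SAP Section 10.3

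*Protocol*

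**What the plan says.** **Sampling.** Protocol Section 17.8.1 puts the PK samples for Visits 3–5 "within 15 min before study agent administration". Note 15 to the Schedule of Events (Section 15) also makes the weekly samples pre-dose, but with a limit of 1 hour before the morning dose. The EOT row of Section 17.8.1 reads "Any time during visit", with a stated preference for the end of the visit. Note 15 agrees ("At the EOT visit, the sample will be collected at any time during the visit") and adds that "the time of the subject's last dose and the time of the PK sample collection will be recorded".

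**Parameter.** Protocol Section 7.2.2.1.1 names one PK parameter, to be summarized descriptively: "Pre-dose concentration of AKST4290 in plasma immediately before administration of the Nth dose".

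**Visit mapping.** Under SAP Section 10.3, when EOT takes the place of a weekly visit, "the measurements of the End of Treatment visit are also used for that scheduled weekly visit". This applies if EOT falls inside the weekly visit's window and that weekly visit was not done. The rule is general and names no exceptions.

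**Reporting.** SAP Section 14 says "AKST4290 concentration values will be reported in a figure, table and listing by analysis time point". It restricts PK to the AKST4290 arm and adopts Protocol Section 17.9.4 (missing values, values below quantification, the two-thirds rule). It sets no condition on time since dose.

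**The concern.** Two kinds of sample follow different timing rules, and a general visit-mapping rule can put them in the same cell of a table. Protocol Section 7.3.3 asks for study drug to be given during the visit, and Section 7.3.3.4 lists study agent administration among the EOT procedures. An EOT sample taken at the preferred moment is therefore likely, though not certain, to follow a dose.

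If such a value is shown as Week 1 or Week 2, the mean for that visit is no longer a mean of pre-dose concentrations, although the schedule tells the reader that it is. With very few subjects on active drug, a single misplaced value can move the mean visibly.

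A related ambiguity is that Section 17.8.1 lists Visits 3–5 as pre-dose, while note 3 to the Schedule of Events makes Visit 5 the EOT visit for subjects who reach Week 3. The same sample then falls under two timing rules.

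**Working it through.** The plan states no figure on this point, so there is nothing to reproduce. The check has two parts.

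**1. How often can the mapping apply?**

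Inputs: the visit windows in Protocol Sections 7.3.3.1, 7.3.3.2 and 7.3.3.4.

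- Week 1: Day 7 ± 2 = Days 5–9
- Week 2: Day 14 ± 2 = Days 12–16
- Week 3: Day 21 ± 2 = Days 19–23

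The windows cover 3 × 5 = 15 days. Days 5 to 23 number 19, and the four not covered are Days 10, 11, 17 and 18. Counting from Day 2 instead gives 15 of 22. In the Week 3 window EOT and Visit 5 are the same visit, so the replacement of a separate weekly visit concerns the 10 days of Weeks 1 and 2.

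These are counts of days, not probabilities. The second condition, that the weekly visit was not done, must also hold. Protocol Section 7.3.3.4 expressly allows EOT to replace the next scheduled visit, so the situation is foreseen.

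**2. How far can one value move a visit mean?**

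Inputs:
- six subjects enrolled (SAP Section 10.1);
- 1:1 allocation (Protocol Section 10.6.1), hence n ≈ 6/2 = 3 on AKST4290. The actual split is not given, so this is an assumption;
- R, the ratio of the carried-over value to the trough. The documents give no such ratio, so it is also an assumption.

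Let all n true troughs equal T and let k carried-over values equal R × T. Then

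mean = [(n − k)T + kRT]/n = T × [1 + k(R − 1)/n],

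so the relative shift is k(R − 1)/n. With k = 1:

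| R (assumed) | n = 2 | n = 3 | n = 4 | n = 15 (as planned) |
|---|---|---|---|---|
| 1 | 0% | 0% | 0% | 0% |
| 1.5 | +25% | +17% | +13% | +3% |
| 2 | +50% | +33% | +25% | +7% |
| 3 | +100% | +67% | +50% | +13% |
| 5 | +200% | +133% | +100% | +27% |

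For example, n = 3 and R = 2 gives (2 − 1)/3 = +33%. R = 1 is the case where the EOT sample happens to be pre-dose. R below 1, for instance a withdrawn subject sampled some time after the last dose, would lower the mean.

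**3. Does another rule remove the value?**

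Protocol Section 17.9.3 uses actual sampling times, but for calculating PK parameters. It does not say which concentrations enter a by-visit table, and SAP Section 14 does not cite it. SAP Section 13.5 keeps Week 3 apart from EOT, but only for pruritus. In the readable text nothing removes the value.

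**The case against.** The best case for the plan has four parts.

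- **The definition excludes the value.** A post-dose concentration does not meet the definition of the pre-dose parameter, and the times needed to identify it are recorded. A careful analyst would leave it out. This is true, but the SAP does not say so, and its one explicit rule on the matter points the other way.
- **SAP Section 14 promises concentrations by time point and does not name a trough summary.** This is correct. The pre-dose meaning of the weekly time points comes from the protocol's schedule and parameter definition.
- **The table shells cannot be seen.** SAP Section 10.12.2 refers to mock tables in Section 18, and the pages after the references are blacked out. A shell may define the PK time points, so the point rests on the readable text.
- **Visit 5 is less ambiguous than it looks.** Sections 7.3.3.1 and 7.3.3.2 mark the sample as pre-dose, Section 7.3.3.4 does not, and note 15 separates weekly visits from EOT. The Visits 3–5 row is probably loose wording, but it still needs to be reconciled.

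A reader might infer more than the documents support:

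- That EOT samples are always post-dose. The text says only any time during the visit.
- That weekly summaries are bound to be contaminated. Nothing is copied if the weekly visit was done.
- That the distortion affects only responders and could create a false link between exposure and response. Visit 5 is EOT also for subjects without disease control at Week 3, early withdrawals are asked for EOT procedures too (Protocol Section 7.3.5), and neither document plans an exposure–response analysis.

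**Conclusion.** Wrong as written, but minor. Followed literally, SAP Sections 10.3 and 14 can place a concentration that is not pre-dose in a weekly pre-dose summary. The shift from one such value is (R − 1)/3 of the trough mean: 0% at R = 1, +33% at R = 2 and +67% at R = 3. This assumes three AKST4290 subjects with equal true troughs. The ratio R is wholly assumed, and the documents do not show that any value was in fact carried over.

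The consequence is confined to an exploratory, descriptive PK endpoint. No efficacy or safety result depends on it. Because concentrations are also listed and the EOT dose and sample times are recorded, an affected value could be traced. The case for acting is that the correction is simple and that a by-visit table from so few subjects is easily misread.

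**What to change.** 1. In SAP Section 10.3 or 14, state that the EOT-to-weekly mapping does not apply to PK concentrations. Alternatively, admit an EOT value to a weekly pre-dose summary only when its recorded times show that it was drawn before that visit's dose.
2. In SAP Section 14, report EOT concentrations as their own time point, with actual hours since last dose shown in the figure and listing.
3. Reconcile the Visits 3–5 pre-dose row of Protocol Section 17.8.1 with Visit 5 being the EOT visit, and say how Visit 5 samples are classed. Any pre-dose filter also needs one stated window, since Section 17.8.1 gives 15 minutes and note 15 gives 1 hour.

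The cost is about two sentences in the SAP plus one clarification. SAP Section 10.1 says all six subjects have completed, so the change affects only how existing samples are classified. Note 15 already requires the EOT last-dose and sample times, so no new data are needed. Once PK is exempted, the shift calculated above is zero.
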